6.1.4 Method of Assignment/Randomization

All participants will receive every flavor/water concentration (4 e-liquids flavors at 4 water concentrations = 16 total manipulations). Participants and research assistants will be blinded to flavors administered. We will use block randomization to determine order flavors are presented in. Water concentration will be presented from hypothesized least irritating to most irritating (20% water, 10% water, 5% water, no alteration).

6.1.5 Blinding and Procedures for Unblinding

A researcher not administering lab session procedures will be responsible for filling e-liquids pods. Our biostatistician, [name], will produce a randomization chart that will be given to the designated researcher and stored in a locked cabinet. Pods will be numbered from 1-4 for each participant corresponding to the participant. Water concentration (which is not blinded for researchers) will be labeled A, B, C, D, with A representing “No water concentration change”, B representing “5% water volume”, C representing “10% water volume”, and D representing “20% water volume”. Participants will be blinded to water concentration. In the event of a serious adverse event, the PI, will consult with Yale Tobacco Center for Regulatory Science (TCORS; the funder of this pilot) co-Is, [name] [name] and [name], along with center chemosensory expert [name] to determine if blind needs to be broken. Given all study participants are administered all e-liquids, the study will be paused during this period.

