5.1 General Design Description

The study is a within subjects' laboratory study, in which participants will complete two laboratory sessions under double blind conditions. Across the study, participants will be exposed to four different e-liquid flavors at a single fixed nicotine concentration (36mg/ml nicotine salt formulation). Three of the e-liquids flavors will be aldehyde containing e-liquids and one flavor will be a non-aldehyde containing flavor and serve as a control. Each flavor will be presented with the following manipulations to its water concentration; (1) flavor as commercially produced, (2) water added so 5% total water volume achieved, (3) water added so 10% total water volume achieved, (4) water added so 20% total water volume achieved. In each lab session, under double blind conditions, participants will sample two of the four flavors at each of the 4 water volumes (i.e. no change to water volume, 5% water volume, 10% water volume, 20% water volume). Participants will be randomized to flavor order and water concentration for each flavor will be presented from hypothesized least irritating to hypothesized most irritating, as is recommended with chemosensory studies.

Figure 1. Diagram of Study Procedures

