completion of baseline assessments, at Lab 1, participants will be familiarized with the sensory and hedonic scales and trained in how to puff the e-cigarette (using non-nicotine and non-flavored e-liquid). Participants will then begin testing procedures for their assigned Flavor 1, which will be administered under double-blinded randomized conditions (see above). For each flavor, participants will take two puffs of the flavor when diluted by four levels of water concentration. Participants will be instructed to take two 3-second puffs with a 30 second inter puff interval. Each two-puff bout will be separated by 10-minutes. These procedures are adapted from our recent work (HIC #2000023077), with the number of puffs is reduced as we are not examining the effects of nicotine and only sensory effects of flavor. Per our current practice we will record timed instructions for each puff bout and participants will be trained to follow these directions. Following each puff exposure participants will complete the General Labeled Magnitude Scale (gLMS) for measures of overall intensity, irritation, coolness and sweetness, the Labeled Hedonic Scale (LHS) for measures of liking, the E-Cig Effects Questionnaire for measures of e-cigarette drug effects, and the Multiple-Choice Questionnaire to assess e-cigarette value. Participants will complete the above procedures for two flavors and four water concentrations for each flavor during each lab session. For each flavor, water concentration order will not be randomized and will be presented from hypothesize least irritating (20% water concentration) to hypothesized least irritation (e-liquid as commercially available with no water dilution) to a) maintain consistency of presentation of water concentration across flavors and b) to avoid potential irritation effects from hypothesized more irritating products to less irritating products. Following at least 24 hours, participants will repeat procedures with the remaining two flavors. Each lab session will last approximately two hours.

Debrief

At the end of Lab 2, participants will be thanked for their participation and ask to evaluate the four flavors they sampled (i.e. guess what flavors they tried, what nicotine concentration they e-liquids were) and will be given information from the CDC on e-cigarette cessation.

Table 1. List of Study Assessments

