7.1 Ethical Considerations: Informed Consent/Accent and HIPAA Authorization

The study will be conducted in accordance with the conducted in accordance with the ethical principles that have their origin in the Declaration of Helsinki.

Participants will not be told of the flavors administered, the water concentration administer, or the nicotine concentration of the product. They will be told that products containing moderate levels of nicotine, flavorings that do or do not contain components considered "flavor aldehydes" and that we will be adding water to some of the formulations they will be trying. We will inform participants of this in the consent and indicate that we do not plan to tell them as we do not want prior perceptions of nicotine content or flavors to influence their experience with the product. Participants will be asked not to sign consent if they are uncomfortable with this.

Participants will be compensated \$50 for completing both parts of intake (\$30 for remote portion, \$20 for in person portion). This is commensurate to other e-cigarette studies in our labs. Participants will be compensated \$75 for each laboratory session that is approximately 2 hours in length. Additionally, participants are asked to abstain from vaping for 2 hours prior to each lab session, so this compensation is included. Additionally, at in person appointments, participants will be compensated for travel with \$25. This is the equivalent of the cost of a rideshare in the greater New Haven area to and from our appointment space. Given the short duration of the study and participant preference in previous vaping studies, all compensation will be provided in cash.

The only potential unknown condition identified by the study team that could be discovered as a result of study procedures would be EVALI, due to increased health monitoring for EVALI symptoms. This is included as an added study benefit. During the study, they will be monitored for EVALI related symptoms. Any endorsement of EVALI symptoms that does not have a clear related and proximal cause will result in withdrawal and participants will be referred to a primary care provider.

No information from this study will be added to participant medical records.

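### The sessions are called double blind, but staff are blinded to flavor only; water concentration, the one factor named in the primary models, is open to researchers through fixed A–D codes in a fixed order.

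*Combined protocol and SAP*

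**What the plan says.** Section 5.1 states that "participants will complete two laboratory sessions under double blind conditions". It repeats the label in the sentence that lists the two flavors and four water volumes sampled in a session.

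The detailed sections are narrower:

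- **6.1.4:** "Participants and research assistants will be blinded to flavors administered". Flavor order is block-randomized. For water, "Water concentration will be presented from hypothesized least irritating to most irritating (20% water, 10% water, 5% water, no alteration".
- **6.1.5:** "Water concentration (which is not blinded for researchers) will be labeled A, B, C, D". A means no change, B 5%, C 10% and D 20%. The same section adds: "Participants will be blinded to water concentration".
- **6.1.7:** someone not involved in running the sessions fills the pods and labels each with the study ID, a flavor number and the water letter. The research assistant running the session takes those pods from the locked container. The section ends by saying that research staff will hold the randomization list.
- **6.3:** Flavor 1 is "administered under double-blinded randomized conditions". Water order is expressly not randomized. The debrief after Lab 2 asks participants to guess flavor and nicotine concentration, but not water.
- **6.4.1 and 6.5.1:** the primary mixed models name water concentration as the within-subject factor, and a significant main effect of condition counts as support.
- **7.1:** participants are told that "we will be adding water to some of the formulations they will be trying".

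**The concern.** A reader of 5.1 will take the test of water concentration to be double blind. It is not. Flavor, the factor hidden from staff, enters only the secondary analysis (6.5.2), while the factor known to researchers is the one the primary models test.

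The outcomes are subjective ratings collected in observed sessions. Staff who know the water level could cue participants without meaning to. Staff are meant to be blind to flavor, so such cueing would tend to act on all four flavors alike. A shift common to all flavors appears as a main effect of water, which is the plan's criterion for support.

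Participants know that some liquids have added water, and they meet the same sequence four times. The letters recur as D, C, B, A within each flavor, and the plan does not say that they are hidden from participants. Nothing in the plan checks whether the participant blind held.

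Section 3.2.2 says the results are meant to inform the FDA, so the description of the blind needs to be accurate.

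**Working it through.** **Inputs.** 30 participants (5.3.1); 4 flavors and 4 water levels (6.1.4); code meanings (6.1.5); pod labels (6.1.7); water order (6.1.4, 6.3); model factor (6.4.1, 6.5.1).

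**Step 1: who is blinded to what.**

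| Factor | Participants | Session staff | Place in the analysis |
|---|---|---|---|
| Flavor | Blinded (6.1.4) | Blinded (6.1.4), subject to the list in 6.1.7 | Factor in the secondary models only |
| Water | Blinded (6.1.5) | Not blinded (6.1.5) | Only factor named in the primary models |

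Section 6.1.5 speaks of researchers in general. That this includes session staff follows from 6.1.4, which limits the research assistants' blind to flavor, and from 6.1.7, where the assistant handles pods that carry the letter.

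**Step 2: extent.** The plan's own figure is reproduced: 4 flavors × 4 water levels = 16 conditions. Then:

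- bouts run with the water level open to researchers: 30 × 16 = 480, which is all of them;
- participant-by-flavor series: 30 × 4 = 120;
- possible water orders: 4! = 24, of which 1 is used in all 120 series.

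These figures count exposure to the risk. They do not measure bias.

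**Step 3: can the analysis remove an effect that follows the sequence?** Build a design matrix with an intercept, 3 water indicators and 3 within-flavor position indicators, giving 1 + 3 + 3 = 7 columns. Under the fixed order its rank is 4, the same as with water alone (1 + 3 = 4), because each water level always falls in the same position. An expectancy effect that tracks the sequence cannot be separated from a water effect by any model. For illustration only, a balanced Latin-square order gives rank 7 of 7. This aliasing is a separate matter of order confounding, and relabelling pods leaves it unchanged. It matters here only because it rules out adjustment afterwards.

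**Step 4: direction.** Section 4.1 predicts that irritation falls as water rises in the aldehyde flavors. It predicts nothing for appeal. Section 4.2 asks whether appeal decreases, and section 2.2 treats a loss of appeal as undesirable. An expectancy that favours the hypothesis can therefore be argued for irritation only.

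**The case against.** The strongest reply is that the plan hides nothing: 6.1.4 and 6.1.5 say who is blinded to what. Participants are the raters, and they are stated to be blinded to water. They enter gLMS and LHS ratings by mouse on a monitor (6.2.1), and the puff instructions are recorded (6.3). These safeguards stand and rule out a claim of staff scoring. They are partial, because 7.5 has research assistants administer all questionnaires and the plan does not say who enters the E-cig Effects and Multiple Choice responses.

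A reader might also infer more than the documents support:

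- **That 6.3 contradicts 6.1.5.** In 6.3 the double-blinded phrase describes the assigned flavor, which fits 6.1.4. It needs clarifying, but the overstatement is in 5.1.
- **That bias favours the hypothesis on every primary outcome.** Only irritation has a directional hypothesis. Nor do the documents say that session staff are told the hypothesis, or that participants are told the direction or order of the water change.
- **That participants will learn the pattern.** This is plausible but not shown. No feedback on water level is described, and flavor changes after every four bouts.
- **That expectancy would produce the aldehyde-versus-grape difference.** Staff blinded to flavor could not easily push those ratings apart, and a common shift would largely cancel in that contrast. This defence is limited, because the primary models as written name no such contrast.

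The plan also gives reasons for the fixed order: chemosensory practice, consistency across flavors and irritation carry-over (5.1, 6.3). They support the sequence. They do not explain why researchers must know the level or why the codes must be common to everyone.

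**Conclusion.** The point holds as a mismatch between the stated blind and the actual one, for the factor that the primary models test. The study is double-blind for flavor and participant-blind only for water. All 480 planned bouts are affected. The size of any resulting bias cannot be worked out from the documents, and no favourable direction should be claimed for appeal.

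The conclusion rests on two readings. First, the researchers in 6.1.5 include session staff, as 6.1.4 and 6.1.7 indicate. Second, the fixed order in 6.1.4 and 6.3 is the one used. Section 6.1.1 says instead that the dilutions come in randomized order. If that were so, the predictable-sequence part would fall away, but the open A–D codes would remain.

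A reader might infer that new pod codes would make the study double blind for water. They would not: while the order stays fixed and is printed in the protocol, bout position reveals the level to anyone who has read it. The change is worth making as a cheap and partial protection.

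**What to change.** 1. In 5.1, and in every report of results, describe the study as 'double-blind for flavor; participant-blind only for water'. In 6.3, make clear that 'double-blinded' refers to flavor.
2. Replace the A–D pod letters with participant-specific codes, applied by the existing pod filler. Participants then see no repeated letter sequence, and the label no longer cues session staff. State in the protocol that this protects only in part while the fixed order stays known.
3. Add a question on water content to the existing debrief and report the answers. Read them with care, since a correct guess may come from the sensation itself rather than from the sequence.
4. Reconcile the randomized order of dilutions in 6.1.1 with the fixed order in 6.1.4 and 6.3. Reconcile the statement in 6.1.7 that research staff hold the randomization list with the flavor blind in 6.1.4.

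The cost is slightly more labelling work, one debrief question and a less favourable blinding description; no extra staff are needed. For sessions already run, items 2 and 3 come too late, but the corrected description in item 1 applies to all the data.

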6.1.6 Packaging/Labelling

We obtain all of our e-liquids from American e-Liquid Store, which manufactures all its products in Wauwatosa, WI and reports being the first e-liquid manufacturer in the US to obtain the International Organization for Standardization (ISO) 9001:2008 and Current Good Manufacturing practices (cGMP) certification. The e-liquid mixtures (propylene glycol [PG], vegetable glycerin [VG] and either cinnamon, grape, vanilla, or cherry flavorings will consist of concentrated flavorings added to a base liquid which will consist of a commonly used ration of 50% PG and 50% VG. PG is the original base liquid and is believed to produce a throat sensation (“throat hit”) which mimics the feel of smoking a cigarette. VG is included to enhance the volume of vapor production, giving a greater sensory illusion of smoking.

E-cigarette device to be used is the Suorin iShare auto battery and Suorin iShare replacement pods will be used. This e-cigarette is similar in size and function to other commercially available more popular pod style devices. A new e-cigarette device will be used for each subject, and new pods will be used for each experiment.

6.1.7 Storage Conditions

In order to ensure that we have adequate amount of e-liquid, of the same constituency, we will purchase large quantities of these solutions prior to starting these experiments which will be stored at and dispensed at John Pierce Labs. Pods will be filled with e-liquid mixtures at John Pierce Labs.

After the e-liquids are received, they will be delivered and stored in a controlled and dark laboratory environment housed in the analytical core of the Yale TCORS (PI: [name]), which is a secured building. The liquids will be kept in a locked storage container in a drawer within the lab room before manipulation. [name], chemist on the analytical core of the TCORS, and co-PI of this pilot (on a non-human project arm not detailed in the current protocol), will perform water manipulations (see above 6.1.2) to e-liquid containers. Once complete, e-liquids will be immediately transported to Pierce Labs, which is a secure building, where they will be delivered and stored in appropriate light/temperature conditions.

On the day prior to the lab sessions, a research assistant/associate/fellow who is not involved in the actual conduct of the lab sessions will fill the e-cig pods with the appropriate doses. The information on randomizations to flavor order for lab sessions will be generated by study biostatisticians prior to study start. This information is stored for each participant in an individual envelope and a printed study ID on the cover. These envelopes are stored at Pierce lab along with the purchased e-liquids. The individual filling the pods will be notified of which subject ID number needs to be filled and they will then go to Pierce labs and open the envelope and fill the sixteen pods with the appropriate e-liquids. First, they will label each pod with the study ID number and 1A, 1B, 1C, 1D, 2A, 2B, 2C, 2D if Lab 1 or if 3A, 3B, 3C, 3D, 4A, 4B, 4C, 4D if Lab 2. Each bottle of e-juice will be shaken vigorously prior to filling the pods. Next, they will open the top of the pod and using a mechanical pipette will load .9ml into the pipette from the e-juice bottle and carefully transfer it into the pod. Each pod is then stored in a separate airtight bag to avoid cross contamination of flavors. The individual bags are then stored together in a larger bag labeled with the study ID number and stored back in the locked container until the lab is set to begin. Once the research assistant is ready to begin each lab, they will open the locked container, take the appropriate pod(s) out and leave the others. At the end of the lab, they will return the pod(s) used that day to their proper bag and again return it to the lock box. None of the e-juice or pods will be transported outside of Pierce lab. The research staff will have the group randomization list and will dispense the appropriate e-liquid needed for each subject.

6.1.8 Concomitant therapy

N/A

6.1.9 Restrictions

There are no restrictions.

6.2 Assessments

6.2.1 Efficacy

To evaluate the efficacy of manipulating water content on irritation reduction and its potential impact on appeal, we will use the following assessments:

- 1. General Labeled Magnitude Scale (gLMS):** gLMS ratings will be obtain following each 2-puff puff bout. Participants will rate overall intensity, sweetness, coolness, irritation using the gLMS which is a category ratio scale with 7 semantic labels: "no sensation", "barely detectable", "weak", "moderate", "strong", "very strong", and "strongest imaginable". The labels are positioned quasi-logarithmically according to their empirically determined semantic magnitudes²². The gLMS will be displayed on a monitor via a custom LabView® program, and participants will make their ratings using a mouse. Ratings are numerically transformed and then used for statistical analyses. **gLMS irritation will be used to assessed change in irritation (primary outcome), and intensity, sweetness, and coolness will be used to assess change in overall appeal (primary outcome).**
- 2. Labeled Hedonic Scale (LHS)²³:** Liking will be assessed after following each 2-puff puff bout using the LHS scale. The LHS is a bipolar scale with "neutral" in the middle and 5 symmetrical semantic labels: "like/dislike slightly", "like/dislike moderately", "like/dislike very much", "like/dislike extremely", "most liked/disliked imaginable", positioned on the scale according to their semantic magnitude. The LHS yields ratio-level data on the magnitude of liking/disliking of sensation equivalent to that produced by magnitude estimation (ME). This scale will also be displayed on a computer screen as above and numerically transformed. **LHS will be used to assess change in overall appeal (primary outcome).**
- 3. E-cig Effects (Adapted from Drug Effects Questionnaire (DEQ²⁶):** A modified version of the Drug Effects Questionnaire ^{24,27} will be used in which participants will rate

acute responses to the e-cig on a 0 to 100 mm scale, from “not at all” to “extremely.” Following each 10-puff bout, we will assess E-cig Liking/Wanting (average of “I feel good e-cig effects”, “I want more of that e-cig I received”, “I feel the e-cig strength” and “I like the e-cig effect”). At baseline and following each fixed-dose bout, we will also assess Stimulant effects (average of “I feel energized” and “I feel high”), and Nicotine Withdrawal (average of “I feel sleepy”, “I feel angry”, “I feel irritable”, “I am having difficulty concentrating”, “I feel restless” and “I feel hungry”). **E-cig Effects will be used to assess change in overall appeal (primary outcome).**

4. Multiple Choice Questionnaire to assess e-cig value (Adapted from Multiple Choice Procedure (MCP))^{25,26}: At the end of each 2-puff puff bout, participants will be asked to make discrete hypothetical choices between 10-puffs of the e-cig they had just used or a series of 44 monetary values (\$0.25-\$15.06). The minimum monetary value at which money is chosen over the e-cig puffs is a contingency-based estimate of e-cig value. At the end of each lab session, participants will be given a choice between another 10 e-cig puffs or one of the monetary amounts they picked in the MCPs completed earlier. **MCP will be used to assess change in overall appeal (primary outcome).**

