CLINICAL STUDY PROTOCOL

Interventional Drug or Biologic

Examining the Effect of Varying Water Content of E-liquids on Sensory Experience

Protocol Number

2000031495

NCT05257109

Protocol Version

5-25-22

Version # 3

PRINCIPAL INVESTIGATOR:

Name: [name]

Department: Psychiatry

[contact]

Email Address: [contact]

IND Number:

IND Holder:

NCT Number: N/A

Study Phase (1, 2, 3, or 4-postmarketing):

Confidentiality Statement:

REVISION HISTORY:

Revision #	Version Date
3	5-25-22

Synopsis

Primary Objective

The primary objective of this study is to examine whether (a) sensory irritation and (b) appeal are decreased in e-liquids containing flavor aldehydes (i.e. vanilla, cherry, cinnamon) compared to e-liquids not containing flavor aldehydes (i.e. grape) when the water concentration is increased from the baseline water concentration to the following levels; 5% total water volume, 10% total water volume, 20% total water volume.

Secondary Objective (if applicable)

At each water concentration, we will examine if there are differences in perception of sensory irritation and appeal across the distinct aldehyde containing flavors.

Study Duration

2 years to complete study from HIC submission; we anticipate the subject enrollment period will be 8 months (approximately 1 week/participant). Enrollment began in August 2022, so anticipated subject enrollment will end in March 2023.

Study Design

Within subjects' human laboratory experiment

Number of Study Sites

1; Yale School of Medicine. Yale sites include Connecticut Mental Health Center (intake visits) and John B. Pierce Laboratory (lab sessions).

Study Population

Population is regular e-cigarette users who report use of both nicotine and flavors in their e-cigarettes. We are assessing response to alterations of water level in e-cigarettes among regular users as a potential regulatory tool, so current participants must have regular nicotine experience.

Number of Participants

30; pilot study

Primary Outcome Variables

- (1) Change in irritation at each water level as measured by the Generalized Labeled Magnitude Scale (gLMS)
- (2) Change in appeal at each water level as measured by the Labeled Hedonic Scale (LHS), Drug Effects Questionnaire (DEQ)

Secondary and Exploratory Outcome Variables (if applicable)

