Preliminary (unpublished) evidence from our chemistry lab at the Yale Tobacco Center of Regulatory Science (TCORS) have indicated that it may be possible to reduce acetal formation simply by adding water to e-liquids. This reduces acetal formation by shifting the chemical equilibrium of the formation reaction. Water is physiologically innocuous to inhale via e-cigarette and adding water to e-liquids may be an elegant way to reduce the sensory irritation and cytotoxicity of e-liquids that contain flavor aldehydes. However, adding water also inherently dilutes the flavor and nicotine concentration of the product, which may reduce the appeal overall. This could be a negative outcome if trying to use flavors as a tool to shift combustible cigarette users to potential reduced harm e-cigarettes. However, if irritation is reduced and appeal is not significantly reduced, a regulation requiring a fixed level of water to e-liquids could be a simple and effective tool to reduce potential toxicity in e-liquids with these flavors. *The goal of the proposed study is therefore to determine if the sensory irritation (a marker of potential toxicity) of commercial e-liquids, can be reduced by increasing their water content without adversely affecting flavor appeal in adult e-cigarette users.*

3 Rationale/Significance

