3.2 Purpose of Study/Potential Impact

The goal of the proposed study is to determine if the sensory irritation (a marker of potential toxicity) of commercial e-liquids containing aldehydes compared to a control non-aldehyde

containing e-liquid, can be reduced by increasing their water content without adversely affecting flavor appeal in adult e-cigarette users. Given that adding water to e-liquid is an innocuous manipulation, if irritation is reduced and effect on appeal is limited, this could be a tool for regulation to reduce harm associated with e-cigarettes.

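### Section 6.2.1 counts ratings of sensory magnitude (intensity, sweetness, coolness, perceived strength) as primary appeal, so dilution can be reported as reduced appeal although liking is unchanged

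*Combined protocol and SAP*

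**What the plan says.** Section 6.2.1 gives each instrument a role.

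- **gLMS:** irritation is the irritation outcome. For the other three ratings, "intensity, sweetness, and coolness will be used to assess change in overall appeal (primary outcome". The scale runs from no sensation to the strongest imaginable.
- **LHS** (a bipolar dislike/like scale): "LHS will be used to assess change in overall appeal (primary outcome".
- **Adapted DEQ:** "E-cig Effects will be used to assess change in overall appeal (primary outcome". Its Liking/Wanting score is the mean of four items. Three are hedonic (good effects, wanting more, liking) and the fourth is "I feel the e-cig strength".
- **Multiple-choice monetary value:** "MCP will be used to assess change in overall appeal (primary outcome".

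Three other places define appeal differently. The synopsis has "Change in appeal at each water level as measured by the Labeled Hedonic Scale (LHS), Drug Effects Questionnaire (DEQ". Section 5.2 lists the DEQ, the LHS, gLMS sweetness and the multiple-choice questionnaire, without intensity or coolness. Section 6.5.1 mentions only the LHS, as an example.

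Sections 6.4.1 and 6.5.1 fit a separate mixed model to each measure, with water concentration as the within-subject factor. They give no composite, no hierarchy among appeal measures, no direction for intensity, sweetness or coolness, and no rule for disagreement.

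Section 2.2 concedes that "adding water also inherently dilutes the flavor and nicotine concentration of the product". Section 3.2 states the aim as learning whether irritation "can be reduced by increasing their water content without adversely affecting flavor appeal in adult e-cigarette users".

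**The concern.** The study's conclusion has two halves: irritation falls, and appeal does not. Section 2.2 would see a case for a water requirement if irritation is lower and no significant loss of appeal appears. The second half is only as sound as the measures called appeal.

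A magnitude rating has no valence. A person can find a diluted liquid weaker and like it exactly as much. Because the intervention is itself a dilution, ratings of intensity, and probably of sweetness and strength, are under downward pressure whatever happens to liking. Overall intensity has a second route: if irritation is part of what people rate as intensity, the benefit the study hopes for also lowers an outcome labelled appeal.

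With several primary appeal measures, each tested separately, and no statement of which prevails, a significant fall in intensity beside a flat LHS could be written up as reduced appeal. That could count against a water standard for a purely sensory reason.

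**Working it through.** **The plan's own figure.** Section 6.4.2 says 30 participants suffice for large differences at two-sided 0.05. It gives no SD, correlation, numeric effect or power, so it cannot be reproduced exactly. As a plausibility check, a paired t-test with n = 30 has 98.8% power at a within-person standardized difference of 0.8, and 80% power at 0.53. The statement is plausible. It also means that moderate shifts in a magnitude rating are detectable.

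**Step 1: dilution.** With native water fraction w0 and target w, flavor and nicotine fall to (1 − w)/(1 − w0). Section 6.1.3 uses 1% native water as an example. At 20% water the ratio is 0.80/0.99 = 0.808, so nicotine goes from 36 to about 29.1 mg/ml (treating weight and volume fractions alike). For native water of 0–5% the ratio is 0.800–0.842.

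**Step 2: chance of a significant intensity result, liking unchanged.** Assumptions, none from the documents except the 1% example and n = 30: intensity falls in proportion to dilution; four flavors are averaged; residual log-SD is s; there is no person-by-water variation. The SD of a person's mean change is s√(2/4), so d = −ln(ratio)/(s√0.5), tested by a two-sided noncentral t with 29 df.

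| Water | Ratio | −ln(ratio) | d at s = 0.3/0.5/0.7 | Chance |
|---|---|---|---|---|
| 20% | 0.808 | 0.213 | 1.00/0.60/0.43 | >99/89/62% |
| 10% | 0.909 | 0.095 | 0.45/0.27/0.19 | 66/30/18% |
| 5% | 0.960 | 0.041 | 0.19/0.12/0.08 | 18/10/7% |

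Sensitivity at 20% water:
- Half-proportional response (log contrast 0.213/2): 76/36/21%.
- Full proportionality plus a between-person log-SD of 0.4 in the water effect: SD = √(0.5s² + 0.16) = 0.453/0.534/0.636, giving d = 0.47/0.40/0.34 and about 70/56/43%.
- Native water 5%: −ln(0.80/0.95) = 0.172, giving d = 0.81/0.49/0.35 and about 99/73/45%.

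**Step 3: the irritation route.** Suppose irritation falls by a standardized 0.8 and intensity moves only through its correlation r with irritation. Intensity then falls by 0.8r. For r = 0.3/0.5/0.7 that is 0.24/0.40/0.56, significant in 25/56/84% of trials.

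**Step 4: the strength item.** If strength averages 40–60 mm (assumed) and falls 19%, the four-item mean drops 40 × 0.19/4 = 1.9 mm to 60 × 0.19/4 = 2.85 mm. In standardized terms, a fall of 0.8 in that item alone moves the mean by (0.8/4)/√((1 + 3ρ)/4). For inter-item correlation ρ = 0.2/0.5/0.8 this is 0.32/0.25/0.22, with power 39/27/21%.

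**Step 5: the whole set.** A simulation took six appeal measures (intensity, sweetness, coolness, Liking/Wanting, LHS, monetary value), correlation 0.5, with liking, value and coolness unchanged. Intensity, sweetness and strength each fell by d. At least one measure fell significantly in 52%, 89% and >99% of trials at d = 0.3, 0.5 and 0.8. With no change in anything the figure was 10%. With LHS and monetary value only, it was 4–5% throughout, close to what two tests at 2.5% in the adverse direction would give.

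**The case against.** A reader might infer that a fall in these ratings will be read as lost appeal, or that lower irritation with preserved appeal is close to impossible to show. The documents do not support either.

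- No direction is set for intensity, sweetness or coolness, and nothing says that one fall among the measures means appeal is lost. Each has its own model, so the LHS and the monetary value would still show unchanged liking. This stands, and limits the point to what can be reported. It does not say which result prevails.
- Intensity and coolness count as appeal only in 6.2.1. This stands. But 6.2.1 is the section that gives every rating its role, and nothing says another section overrides it.
- The high probabilities belong to 20% water under favorable assumptions. At 5% and 10% water, or with a weaker or more variable response, they fall a long way. This stands.
- Section 4.2 contrasts aldehyde flavors with grape, and a dilution effect common to all flavors would cancel from that difference on the log scale. The planned primary models, however, name water alone as the factor.
- Section 2.2 links sweet taste and cool flavors to appeal, and section 3.2.2 links lower delivery to lower appeal. That makes these attributes possible drivers of appeal, which is not the same as measures of it.
- None of the four flavors is described as cooling, so coolness probably sits near its floor. It would be uninformative rather than biased. The irritation route is argued only for overall intensity.
- The strength item is one of four and rarely moves the average alone (step 4). Reporting the score both ways is enough.

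**Conclusion.** The point holds as a problem of measurement and of an unresolved outcome definition. As written, 6.2.1 lets a sensory effect of dilution, or for overall intensity the fall in irritation itself, be recorded as reduced appeal with liking unchanged. The exposure is greatest for intensity, less for sweetness, small for the strength item, and not shown for coolness.

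Its size is uncertain because the documents give no variances, correlations or dose-response for any rating. Under the proportional model it ranges from about 7% (5% water, log-SD 0.7) to above 99% (20% water, log-SD 0.3). It is a serious possibility at 20% water, moderate at 10% for the smaller SDs, and slight at 5%. The figures show that the classification matters; they do not predict the trial's result.

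**What to change.** 1. Align the definition of appeal in the synopsis and in 5.2, 6.2.1 and 6.5.1.
2. Name the LHS as the primary appeal outcome, with the multiple-choice monetary value and Liking/Wanting as supporting appeal measures. This ordering also settles which result leads when they disagree.
3. Treat gLMS intensity and coolness (in 6.2.1) and sweetness (in 6.2.1 and 5.2) as secondary sensory descriptors.
4. Report Liking/Wanting with and without the strength item, and show strength separately.

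The cost is wording and scoring. Fewer measures carry the appeal label, and the sensitivity version of the adapted score has three items instead of four. All the ratings are already collected, so no new data are needed. The change is best made before unblinded analysis.
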